1.3 Study design

PHARM-CHF is a prospective multicentre, randomized controlled study.

The following inclusion criteria are defined:

- Age: 60 years and older
- Diagnosis of chronic heart failure (CHF)
- Stable* CHF medication including a diuretic (thiazide, loop diuretic and/or MRA). *Stable CHF medication is defined as no relevant change of HF medication in terms of drug therapy started/terminated or dose change, especially of (loop-)diuretics within past 4 weeks.
- Hospitalization for decompensated heart failure within past 12 months or a value of B-type natriuretic peptide (BNP) ≥ 350 pg/mL or N-terminal pro-B-type natriuretic peptide (NT-pro-BNP) ≥ 1400 pg/mL
- Written informed consent

The following exclusion criteria are defined:

- Regular/assisted use of a weekly dosing aid
- Unwillingness or inability to visit the participating pharmacy once a week
- Planned cardiac surgery
- Life-expectancy < 6 months
- Unwillingness or inability to comply with the study protocol (including drug abuse or alcohol dependency)
- Participation in other studies (currently or in the last 4 weeks)

No subject will be allowed to be enrolled in this study more than once.

In the following table, the visit schedule is shown. Visit 2 and visit 4 will be performed as telephone visits; the other visits will be performed at the medical practices.

Table 1 Visit schedule and data collection

	Screening / V1 (month 0)	V2 (after 6 months)	V3 (after 12 months)	V4 (after 18 months)	V5 (after 24 months)	V6 (end of study)
In- and exclusion criteria	X					
Heart failure (leading cause, duration)	X					
CV-risk factors	X		X		X	
Sociodemographic data	X					
Height	X					
LVEF (if available)	X					
DMP participation	X		X		X	
Medical history	X		X		X	
Device treatment	X		X		X	
Medication list	X		X		X	
NYHA class	X		X		X	
Care level (Pflegestufe)	X		X		X	
Blood pressure	X		X		X	
Pulse	X		X		X	
Weight	X		X		X	
Documentation of laboratory values	X		X		X	
Hospitalization		X	X	X	X	X
Quality of life questionnaire (MLHFQ)	X		X		X	
Patient health questionnaire (depression module, PHQ-9)	X		X		X	
Self-estimated medication adherence (scale 0-100%)	X		X		X	
Self-reported patient global assessment (PGA)			X		X	

Abbreviations: BNP/NT-proBNP, (N-terminal fragment) brain natriuretic peptide; CV, cardiovascular; EF, ejection fraction; DMP, disease management program; NYHA, New York Heart Association; MLHFQ, Minnesota Living with Heart Failure Questionnaire; PHQ, patient health questionnaire; PGA, patient global assessment

Events (hospitalizations and death of any cause) are recorded continuously in the medical practices.

1.4 Randomization

Eligible patients are assigned in a 1:1 ratio to the intervention or control group. Minimization with 20% residual randomness is used to ensure balance of the following characteristics: Gender (male/female), age (≤ 75 , > 75), NYHA functional class (I and II, III and IV), PHQ-9 (score < 10 , ≥ 10), diabetes mellitus (yes/no), study region (according to regional Associations of Statutory Health Insurance Physicians (KV-Region)).

A web-based randomization tool developed by IZKS Mainz is used within this study allowing investigators to randomize patients via a secure web interface.

Subjects withdrawn from the study retain their identification codes (i.e. patient number). New subjects must always be allotted a new identification code.

2 Analysis populations

2.1 Total population

The total set consists of all patients recruited including subjects withdrawn from the study.

2.2 Intention-to-treat population

The intention-to-treat (ITT) population consists of all patients who have post-baseline data available and who did not fail to satisfy major entry criteria. Patients in the intervention arm (with or without withdrawal of consent) for whom no consolidated medication plan is available – that is, subjects failed to comply with the study protocol at entry (i.e. did not undertake the medication review at the pharmacy - which is comparable of not taken any trial medication), have no post-baseline data available.

The following violations of entry criteria are defined as major and will lead to exclusion from the ITT population:

- Violation of inclusion criteria
 - o Hospitalization more than 12 months ago
 - o No diuretic (thiazide, loop diuretic and/or MRA) at baseline
- Patient did not undertake the medication review at the pharmacy
- Meeting any exclusion criteria
- Post baseline data not available

Those violations will be displayed by absolute frequencies.

In the following table, patients with violation of major entry criteria and the intention-to-treat population are shown.

Table 2 Violation of major entry criteria and intention-to-treat population

Population	Intervention group	Control group	Total
Randomized (total population)	130	128	258
- patients excluded: no medication review at the pharmacy/consolidated medication plan not available	17	0	17
- patients excluded: violation of major entry criteria	3	1	4
No diuretic	2	1	3
No hospitalization for decompensated heart failure within past 12 months or no BNP/NT-proBNP level above cutoff	1	0	1
ITT	110	127	237

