### 11.3 Analysis Populations

#### Intention to treat

The intention to treat (ITT) population consists of all patients who have post-baseline data available and who did not fail to satisfy major entry criteria. Patients in the intervention arm (with or without withdrawal of consent), for whom no consolidated medication plan is available i.e., subjects failed to comply with

the study protocol at entry (i.e. did not undertake the medication review at the pharmacy - which is comparable of not taken any trial medication), have no post-baseline data available.

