### **Per Protocol**

The per protocol (PP) population consists of all subjects of the ITT population who completed the study without major protocol violations. These are violation of inclusion criteria, meeting exclusion criteria, post-baseline data not available, consolidated medication plan not available (intervention group patients only) and premature termination (except death). As data for patients withdrawn (with withdrawal of consent) from the study will be anonymized immediately, pseudonymized data acquisition from other sources e.g., health insurance funds is impossible.

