5.4 Hospitalization during study participation and mortality

5.4.1 Documentation

Events (hospitalizations and death of any cause) are recorded continuously in the medical practices. Additionally, health insurance funds will be asked to provide data about hospitalizations. For patients with withdrawal of informed consent no data will be provided by health insurance funds. The different sources and the result of the blinded adjudication by the CEC will be documented.

Apart from hospitalizations and death no further adverse events are collected.

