5.5 Pharmacy claims data from data processing centres and health insurance funds

All known German data processing centres (Apothekenrechenzentren) will be asked to send pharmacy claims data of prescribed medicinal products dispensed at community pharmacies for PHARM-CHF patients to the cost of any statutory health insurance (SHI) funds for the whole study duration and additionally for the measurement of baseline adherence for the 183 days before randomization. In addition, health insurance funds (SHI and private) will be asked to provide data about reimbursed medicinal products dispensed at community pharmacies for the same period. The prescribed medicinal product together with dispensing date and the source of information will be documented.

For patients with withdrawal of informed consent no pharmacy claims data will be available. Therefore, the PDC for these patients cannot be calculated.

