7.1 Timing of final analysis

When all data from the eCRF, the data processing centres and the health insurance funds will be collected, study data will be prepared for determination of the PDC. Afterwards the final analyses will be performed.

Estimated timing of final analysis: February 2019

All outcomes will be analysed collectively.

7.2 **Patient disposition**

The following patient disposition variables will be presented by numbers and percentages for the total, ITT and the PP population:

- Randomized
- Major protocol violations (with details listed)
- Deaths
- Discontinued except death (with reasons listed)
- Time within the study (≥ 12 months) of the patients who died
- Time within the study (≥ 12 months) of the patients who discontinued except death
- Time within the study of all patients

365 days follow-up

- Terminated prematurely
 - Withdrawal of informed consent
 - Discontinuation
- Death
- Completed first 365 days of study

Follow-up between 365 and 730 days:

- Terminated prematurely
 - Withdrawal of informed consent
 - Discontinuation
- Death
- Study duration < 730 days
- Completed 730 days of study

The following patient disposition variables will be presented by sample characteristics for the total, ITT and the PP population:

- Number of events
- Number of unplanned cardiovascular hospitalizations
- Number of unplanned cardiovascular hospitalizations (365 days)
- Number of events per patient
- Time within the study of the patients who died
- Time within the study who discontinued except death
- Time within study overall
- Time within study of patients who terminated the study regularly

The participation on visit 1, visit 3, and visit 5 as well as the possible reason for drop out will be tabulated for the ITT.

The individual duration of study will be calculated for each patient by duration = (date of end of study – date of randomization) + 1 and will be analysed descriptively.

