The primary analysis population for both adjustment types is the ITT population. However, the primary analysis (both adjustments) will be repeated for the PP population for sensitivity. As a further sensitivity analysis an analysis of (co)variance (AN(C)OVA) for the PDC will be done with PDC as dependent variable, and the further fixed effects treatment (intervention vs. control), data from health insurance funds (yes/no), sex (male vs. female), age (≤ 75 vs. > 75 years), NYHA functional class (I and II vs. III and IV), PHQ-9 score (score < 10 vs. ≥ 10) and diabetes mellitus (yes vs. no). The study region will be omitted since this may lead to an over determination of the analysis model.

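### The 'ITT' set drops intervention patients who missed a post-randomisation pharmacy review (17 of 130 v 0 of 128), so the primary comparison is not between the randomised groups

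*SAP*

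**What the plan says.** SAP 2.2 lists, among the violations of entry criteria that exclude a patient from the ITT population: "Patient did not undertake the medication review at the pharmacy". Protocol 11.3 has the same rule. It treats intervention patients without a consolidated medication plan, whether or not they withdrew consent, as having no post-baseline data, because they "did not undertake the medication review at the pharmacy - which is comparable of not taken any trial medication".

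SAP Table 2 gives the count under the label "patients excluded: no medication review at the pharmacy/consolidated medication plan not available": 17 intervention, 0 control. A further 3 v 1 are removed on genuine entry criteria. The set is then 110 v 127.

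SAP 7.8 states: "The primary analysis population for both adjustment types is the ITT population". It repeats the analyses in the per-protocol set (102 v 125, SAP Table 3), which is a subset of the ITT set. All 258 randomised patients appear only in the disposition tables of SAP 7.2. SAP 7.9 names no population for the primary safety analysis. Protocol 11.4.4 describes the per-protocol analysis as additional for all primary and secondary variables, which suggests that the main safety analysis uses the same ITT set.

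Protocol 11.5.3 names intention-to-treat analysis as the protection against bias from intervention patients who do not want to visit the pharmacy.

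**The concern.** An intention-to-treat comparison is protected by randomisation because membership of each group is fixed before anything the patient does afterwards. Here membership of one group depends on attending a pharmacy appointment after allocation is known to patient and physician. Control patients who would also have failed to attend stay in the analysis, while their intervention counterparts are taken out.

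Willingness to attend the pharmacy is plausibly related to medication adherence, which is the primary outcome and the only one the trial is powered for (protocol 11.1). If non-attenders are less adherent, the rule favours the intervention. If they are more adherent, it works against it.

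The protection in protocol 11.5.3 covers patients who start and later stop. It does not cover those who never start.

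**Working it through.** **1. Table 2 reproduces.** Intervention: 130 − 17 − 3 = 110. Control: 128 − 0 − 1 = 127. Total: 237, as printed. Removed by the medication-review rule: 17/130 = 13.1% v 0/128 = 0% (Fisher exact p = 8.8 × 10⁻⁶). This rule accounts for 17 of the 21 exclusions.

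**2. Timing.** Protocol 8.4.2.2.1 places the review appointment within two weeks after randomisation, in the intervention group only. It is not an entry criterion, although SAP 2.2 lists it as one.

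**3. Are data really unavailable for the 17?** PDC comes from data processing centres and insurers (SAP 5.5, 7.8), and events come from practices and insurers (SAP 5.4.1). None of these depends on the pharmacy review. The documents rule the data out after consent withdrawal:
- SAP 5.5: "For patients with withdrawal of informed consent no pharmacy claims data will be available"
- SAP 5.4.1: "For patients with withdrawal of informed consent no data will be provided by health insurance funds"
- Protocol 11.3, giving the reason: "As data for patients withdrawn (with withdrawal of consent) from the study will be anonymized immediately"

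The exclusion, however, applies with or without withdrawal of consent. For those of the 17 who did not withdraw, the absence of data is declared by definition.

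**4. Size of the bias, by assumption.** Let *g* be the amount by which mean PDC in the 17 falls below that of the 110. Putting the 17 back gives 110 + 17 = 127, so leaving them out overstates the intervention mean by (17/127) × *g*. With the planning SD of 0.22 (SAP 1.2), the standard error of the difference is 0.22 × √(1/110 + 1/127) = 0.02865. If the randomised groups truly do not differ, the rejection rate is P(|Z + bias/0.02865| > 1.96).

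The planned test is a rank test, so an unstratified rank-sum test was also simulated, with 20,000 runs per gap. PDC was beta-distributed with overall mean 0.70 in both arms and SD 0.22 in each subgroup. The control arm held 110 patients of the retained type and 17 of the excluded type; the intervention arm held 110 of the retained type.

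| Assumed gap *g* | Bias | Rejection, test of means | Rejection, rank-sum |
|---|---|---|---|
| 0 | 0 | 5% | 4.9% |
| 0.05 | 0.007 | 5.6% | 5.5% |
| 0.10 | 0.013 | 7.5% | 7.4% |
| 0.20 | 0.027 | 15% | 13% |
| 0.30 | 0.040 | 29% | 21% |

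If the 17 are the more adherent, the sign reverses.

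**5. How much can be recovered.** The documents do not say how many of the 17 withdrew consent. If *k* have obtainable claims, adding them at a gap of 0.20 moves the intervention mean by *k*/(110 + *k*) × 0.20, which is 0.007 (*k* = 4), 0.014 (*k* = 8) or 0.020 (*k* = 12).

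**6. Power after repair** (two-sided t-test, SD 0.22). The planned 88 v 88 at 0.10 gives 85.0%, which reproduces SAP 1.2. Now assume an effect of 0.10 in patients who had the review, and that the 17 sit at control level:
- All 17 recovered, 127 v 127: effect 0.10 × 110/127 = 0.0866, power 87.8%.
- As above, but the 6 v 1 who withdrew consent (SAP Table 3) have no PDC, 121 v 126: effect 0.10 × 104/121 = 0.0860, power 86.4%.
- As in the previous line, but only 4 or 8 of the 17 recovered (108 or 112 v 126): effect 0.0963 or 0.0929, power about 91% or 90%.

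**The case against.** The strongest defence has four parts.

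**Disclosure.** The rule is stated in both documents, counted by arm in Table 2, and will appear in the CONSORT diagram. That is true, and nothing is hidden. But stating a rule in advance does not undo selection after randomisation.

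**Missing data.** SAP 7.8 and 7.10.2 say that insurer data were not available for all patients, without linking this to consent. Processing-centre claims cover statutory insurance only, so privately insured patients depend on their insurer. Some of the 17 may therefore be unrecoverable even without withdrawal, and if most withdrew, deleting the criterion changes little. The event counts planned for all randomised patients in SAP 7.2 do not prove that follow-up data exist for the 17. All this stands as a limit on the repair. It does not justify the exclusion: controls with incomplete insurer data are kept, the plan already stratifies on insurer data (yes/no), and it calls PDC incalculable only after consent withdrawal.

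**Baseline adjustment.** The second PDC analysis adjusts for baseline adherence. If the gap is 0.20, existed wholly before randomisation, and baseline and follow-up PDC correlate at 0.3, 0.5 or 0.7 (assumptions), rejection falls from 15% to about 10.5%, 8.4% or 6.8%. A gap that arises after randomisation gets less relief or none. Baseline tables by arm (SAP 7.5) could give an indirect sign of selection but cannot measure the bias.

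**Overstated rates.** The 29% at a gap of 0.30 uses SD 0.22 in the control arm, although a mixed arm is wider; allowing for that gives about 27%. The rank-sum figure of 21% is closer to the planned test. The point is fair and leaves the conclusion unchanged.

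**Conclusion.** The concern holds. The population labelled ITT is a modified ITT set, defined by an event after randomisation that can occur in one arm only. Neither the primary PDC analyses nor their planned sensitivity analyses compare the groups as randomised. The imbalance, 17/130 v 0/128, is a fact in the SAP.

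The size and direction of the bias are unknown. The figures above rest on an assumed gap and the planning SD, and with no gap there is no bias. This must be corrected, because it affects the primary analysis of the only powered variable and no planned analysis would measure its effect. The sample size is not at fault, and the 3 v 1 exclusions on entry criteria are a separate, smaller matter.

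**What to change.** 1. Delete the medication-review and consolidated-plan criterion from the ITT definition in SAP 2.2 and protocol 11.3. Analyse as randomised every patient with obtainable outcome data, whether or not the review took place.
2. For patients who did not withdraw consent, use claims, insurer and practice data to day 365 or death, following Version 1 of SAP Table 4 and not cutting at discontinuation.
3. Rename the 110/127 set modified ITT (intervention started) and keep it as a sensitivity analysis.
4. For patients whose PDC is lost through consent withdrawal (any among the 17, plus the 6 v 1 in SAP Table 3), add a tipping-point analysis by arm or a worst-rank analysis. Worst rank penalises the arm with more withdrawals, so read it as a bound. SAP 6.1 at present substitutes no missing values.
5. Report how many of the 17 withdrew consent and, where obtainable, their 183-day baseline PDC beside that of the 110.
6. Name the same population for the primary safety analysis in SAP 7.9.

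The cost is wording in two documents, some extra analyses, and a claims request for those of the 17 who did not withdraw, unless the request described in SAP 5.5 already covers them. No new patients are needed. The estimated effect may become smaller, but power stays at about 86% or more under the assumptions in step 6 of the working.

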2.3 Per-protocol population

The per-protocol (PP) population consists of all subjects of the ITT population who completed the study without major protocol violations – that are violation of inclusion criteria, meeting any exclusion criteria, post-baseline data not available, consolidated medication plan not available (intervention group patients only) and terminated the study prematurely (except death).

The following protocol violations are defined as major and will lead to exclusion from the PP population:

- Terminated the study prematurely (except death) within the first twelve months

This will result in the following sizes of the analysis populations:

Table 3 Major protocol violation and per-protocol population

Population	Intervention group	Control group	Total
Randomized	130	128	258
ITT	110	127	237
- patients excluded: termination within the first twelve months	8	2	10
withdrawal of informed consent	6	1	7
discontinued	2	1	3
PP	102	125	227

2.4 CONSORT flow diagram

The CONSORT flow diagram displays the number of randomized patients, patients included in the ITT population and PP population. This will be displayed overall and for each group (IG/CG) separately. For each group the reason and number of patients affected for exclusion from the ITT population and PP population will be presented.

3 Scope

The main analysis comprises the eCRF data and pharmacy claims data of prescribed medicinal products dispensed at community pharmacies from data processing centres (Apothekenrechenzentren) and health insurance funds (GKV/PKV) and data from health insurance funds about hospitalizations. The main analysis will be performed by the IZKS Mainz. The PDC will be determined by the pmv research group (University Cologne) and will be submitted to the IZKS Mainz for further analyses. Analyses regarding the intervention in participating pharmacies like analyses of drug-related problems (DRPs) and medication discrepancies are based on the eCRF and data documented during the intervention from pharmacists. These analyses will be performed by the Department of Medicine, ABDA, Berlin.

4 Study centers and study regions

In total, 258 patients have been recruited. 130 patients were randomized into the intervention and 128 in the control group. 110 patients from the intervention group and 127 patients from the control group could be included in the ITT population.

In total, 31 study centres (family physicians/GPs, internal medicine specialists, and both office- and hospital-based cardiologists) and 69 community pharmacies are taking part.

Pharmacies and physicians from nine different Federal States of Germany are taking part – that is, Baden-Württemberg, Bayern, Rheinland-Pfalz, Niedersachsen, Nordrhein-Westfalen, Saarland, Sachsen, Sachsen-Anhalt und Thüringen.

5 Variables

5.1 Timing of the data completion

Estimated data completion date: June 2018

5.2 Participating physicians and pharmacies

Minimization is used to ensure balance of study regions. Therefore, the study region will be automatically documented at screening. The participating physicians will be assigned to their specialist's group.

5.3 Demographics and patient characteristics

The following demographic variables will be documented at screening / visit 1:

- Sex (male / female)
- Date of birth
- *Derived: Age [years] = Date of screening – date of birth*
- *Derived: Age will also be categorized as ≤ 75 years and > 75 years*
- Height (cm)
- *Derived: BMI = weight [kg] / (height [cm] / 100)²*
- *Derived: The BMI will also be categorized as underweight (< 18.5 kg/m²) / normal (between 18.5 kg/m² and 25 kg/m²) / overweight (≥ 25 kg/m²)*

The following baseline characteristics will be documented at screening / visit 1:

- Informed consent available (yes/no)
- In- and exclusion criteria
- Randomization result
- Main reason for chronic heart failure (ischaemic, non-ischaemic, other)
- Date of first diagnosis of chronic heart failure (month/year)
- *Derived: Time since first diagnosis [years] = date of screening - date of first diagnosis of chronic heart failure (month/year)*
- Date of last hospitalization due to acute cardiac decompensation
- *Derived: Time since last hospitalization [years] = date of screening - date of last hospitalization due to acute cardiac decompensation*
- *Derived: The time since the index hospitalization will be classified as < 3 months and ≥ 3 months*
- Left ventricular ejection fraction (LVEF, %) at baseline, if available. The LVEF will also be categorized as $< 40\%$ indicating HF_rEF, 40% - 49% indicating HF_{mr}EF, $\geq 50\%$ indicating HF_pEF

The following characteristics will be documented at visits 1, 3, and 5:

- Weight (kg)
- Blood pressure (systolic blood pressure, diastolic blood pressure [mmHg])
- Pulse at rest [/min]
- Care level (Pflegestufe; none/1/2/3/missing/unknown)
- Attendance at Disease Management Program (DMP) KHK (yes/no)
- Attendance at DMP KHK – module heart failure (yes/no)
- Heart pacemaker incl. ICD/CRT (yes/no/unknown) (if yes, with or without a defibrillator)
- New York Heart Association Functional Classification (NYHA class I, II, III or IV)
 - *Derived: The NYHA class will also be categorized as I/II and III/IV.*
- Smoking status (smoker, non-smoker, former smoker)
- Minnesota Living with Heart Failure Questionnaire (MLHFQ) (total score)
 - *Derived: physical and emotional sub-scores, total score at baseline will be categorized as < 24, between 24 and 45, > 45)*
- Patient Health Questionnaire PHQ-9 (total score)
 - *Derived: The PHQ-9 total score at baseline will be categorized as < 10 and ≥ 10*
- Medication adherence (self-reported) (0%-100% in 5% steps)
- PDC
 - o PDC at Baseline (183 days)
 - o PDC ACEI/ARB at Baseline (183 days)
 - o PDC BB at Baseline (183 days)
 - o PDC MRA at Baseline (183 days)
 - o PDC statins at Baseline (183 days)
 - o *Derived: all PDC-values will be categorized as: < 80% and ≥ 80% and < 88% and ≥ 88%*
- Current diagnoses including CV risk-factors (diabetes mellitus, hypertension, hyperlipidemia, family anamnesis of coronary heart disease, coronary heart disease, condition after myocardial infarction, cardiomyopathy, valvular disease, atrial fibrillation, chronic renal disease, COPD, stroke/TIA, depression, malignant tumor, peripheral arterial occlusive disease, sleep apnea, asthma, and further diagnoses)
- Laboratory parameters (HbA1c [%], potassium [mmol/l], creatinine [mg/dl], total cholesterol [mmol/l and mg/dl], HDL-cholesterol [mmol/l] and mg/dl], LDL-cholesterol [mmol/l and mg/dl], triglycerides [mg/dl], BNP, if available [pg/ml], NT-proBNP, if available [pg/ml], urea [mg/dl])
 - *Derived: The GFR will be calculated using the Cockcroft and Gault formula*
- Medication plan (eCRF - physician)
 - o *Derived: number of drug classes, number of drug packages, number of drug substances, number of single doses per day, number of drug intakes per day*
- First consolidated medication plan (intervention group – pharmacists, visit 1)

- *Derived: number of drug classes, number of drug packages, number of drug substances, number of single doses per day, number of drug intakes per day*

